## 1. Visit schedule

Table 1: Visit schedule

Visit schedule	V1 M1-M3 (Baseline)	V2 M4-M8* (Follow-Up)	V3 M9-M14 (Closure)
Demographic data			
Age	x		
Gender	x		
Place of residence	x		
Social characteristics			
Employment status	x		
Marital status	x		
Education level	x		
Living arrangement	x		
Disease history			
Date of disease onset	x		
Date of initial diagnosis	x		
Age at disease onset	x		
Duration of disease	x		
Date of death (if applicable)			
Family history			
Family members who are living with ALS	x		
Family members who died of ALS	x		
Family members who are living with FTD	x		
Family members who died of FTD	x		
Family members who are suffering from neurological/psychiatric disorder	x		
Family members who died of any neurological/psychiatric disorder	x		
Clinical classification			
ALS subtypes	x		
Region of onset	x		
Functional deficits and progression			
ALS Functional Rating Scale (ALS-FRS)	x	x(2)	x
ALS progression rate (loss of ALS-FRS per month)	x	x(2)	x
King's classification of clinical stages of ALS	x		x
Serum neurofilament light chain (sNFL)	x	x(2)	X(2)
Interventions and health care measures			
Use of PEG	x		x
Use of non-invasive ventilation	x		x

Use of tracheotomy	x		x
Provision of a manual wheelchair (1)	x		
Provision of complex power wheelchair (1)	x		
Provision of a communication device (1)	x		
Provision of assistive technology (1)	x		
Physical, occupational and speech therapy (1)	x		
Riluzol and symptomatic pharmacotherapy (1)	x		
Treatment expectation			
MYMOP2, measure yourself outcome profile	x	x(2)	x(2)
Molecular genetic analysis			
C9orf72	x		
FUS	x		
SOD1	x		
TARDP	x		

M: month, V: visit; 1 = subgroup of users of APST management platform, 2 = in subgroup of patients with SOD1 mutation data will be collected more frequently (up to monthly collection of existing data of sNfL; up to weekly self-assessment of ALS-FRS using the ALS-App in addition to on-site assessment of ALSFRS-R during site visits). In the main cohort of non-SOD1 patients the collection of sNfL data is limited to the visits V1 (baseline) and V2 (follow-up).

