### **4.3. Overall study duration and assessments**

The study will include ALS patients at specialized outpatient clinics (study sites). All subjects will undergo 3 assessments over a period of approximately 12 months. The assessment schedule will be as follows:

- Assessment at baseline: initial assessment of subjects including blood sampling and molecular genetic analysis
- Assessment at follow-up: follow-up assessment that is realized in a 6-month interval
- Assessment at the end of the study: final assessment after 10 to 14 months interval and optional

  

- Assessment for interim analysis: interim analyses performed for this study at variable time points, at least after all subjects complete the 6-month assessments.

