### **5.3. Exclusion criteria**

- Inability to provide patient's directives about the notification of individual study results on genetic variants of SOD1, C9orf72, FUS and TARDBP
- Inability to comply with study requirements
- Unspecified reasons that, in the opinion of the site investigator, perceiving the subject unsuitable for enrollment

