### **8. Study procedures and data processing**

#### **8.1. Study procedures**

Subjects will be registered at baseline, after the investigator has verified the eligibility of the subjects by means of inclusion and exclusion criteria. After obtaining informed consent, all data defined in the protocol will be collected from different sources:

- Data capture from medical records (registry): clinical characteristics, family history, interventions and health care measures
- Assessment and data capture at study site (on-site assessment): clinical characteristics, family history, interventions and health care measures, self-assessment scales (ALS-FRS, MYMOP)
- Assessment and data capture from remote (digital self-assessment): self-assessment scales (ALS-FRS, MYMOP)
- Assessment and data capture at molecular genetic laboratory (genetic analysis): genetic variants in the genes of SOD1, C9orf72, FUS and TARDBP
- Capture from APST platform (registry): provision with assistive technology devices

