Given the potential, diagnostic and therapeutic relevance of individual study results on genetic variants of SOD1, C9orf72, FUS and TARDBP genes, all study participants are offered the principal option to be informed about the result of genetic investigation. Conversely, the knowledge and awareness about own study results – encompassing the potential implications for genetically related family members – might be perceived as psychologically burdensome. Therefore, study participants will be informed about the requirement to select between notification options of their individual study results. Study participants who decided to be notified about the genetic study results are offered to seek genetic consultation prior to the notification of study results. The offered genetic consultation will include the information on the mutation type, the interpretation of results (benign, likely benign, likely pathogenic, pathogenic or variant of uncertain significance) as well as the potential medical, psychological and social implications of the findings. The procedure of genetic counseling is described in more detail in section 12.3.3. Study participants will be informed that genetic study results of uncertain significance may be discussed within the genetic review board which is described in section 10.3. The patient's directive concerning the notification about the individual study results is subject to the study information and mandatory part of the informed consent. Study participants are requested to select one of the following options of notification about individual study results:

- No notification about genetic study results
- Notification about all genetic study results
- Notification about selected genetic study results with therapeutic relevance

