Patients who refuse to be notified about study results will not be informed about the outcome of genetic analysis. This patient's directive explicitly includes pathogenic mutations that might be of diagnostic or therapeutic relevance. The patient's directive of notification of all genetic study results will include normal findings (no or benign variants) genetic, genetic variants of unknown significance and pathogenetic mutations (likely pathogenic or pathogenic genetic variants in the investigated genes of SOD1, C9orf72, FUS and TARDBP. Results of diagnostic relevance are defined as genetic variants being known to cause ALS or can increase the risk of ALS or can modify the phenotype of the disease including the progression rate. The finding of pathogenic variants can lead to the diagnosis of fALS although the disorder – given the negative family history of ALS – has prior been classified as sALS. The diagnostic relevance can extend to other family members as likely pathogenic or pathogenic mutations in the study at ALS genes might substantiate a genetic risk for ALS to first- and second-degree relatives of study participants. Therapeutic relevance is defined by the planning or performance of a phase 3 clinical trial, a planned or ongoing early access program or an expected approval of genetic medicine targeting one of the studied genes within the next 12 months. Currently, therapeutic relevance can be stated for mutations found in the SOD1 gene. Therapeutic relevance of C9orf72 and FUS can be expected within the next few years post-approval of this study protocol. The definition of diagnostic and therapeutic relevance and the scheme of notification of individual study results is provided in table 11.

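### Table 1 note 2 assigns up-to-weekly app self-assessment by SOD1 status without reference to the notification directive, so a carrier who refused notification could infer the result

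*Combined protocol and SAP*

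**What the plan says.** **The schedule.** Section 4.3 sets the general plan: "All subjects will undergo 3 assessments over a period of approximately 12 months". Note 2 to Table 1 adds a genotype-specific layer: "in subgroup of patients with SOD1 mutation data will be collected more frequently". The part that the patient carries out is "up to weekly self-assessment of ALS-FRS using the ALS-App in addition to on-site assessment of ALSFRS-R during site visits". Table 1 also puts marker 2 on MYMOP2 at V2 and V3, another self-assessment scale, although the note gives it no frequency. The sNfL part of the note is monthly gathering of values that already exist. For non-SOD1 patients the note restricts sNfL to V1 and V2; it states no app frequency for them.

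**The directive.** Section 5.3 excludes anyone who cannot give "directives about the notification of individual study results on genetic variants of SOD1" and the other three genes. Section 12.3.1 makes the choice a mandatory part of consent and offers three options, one of which is "No notification about genetic study results". The commitment that follows is categorical: "Patients who refuse to be notified about study results will not be informed about the outcome of genetic analysis". The same section extends it to pathogenic mutations of diagnostic or therapeutic relevance, and states that therapeutic relevance currently exists for SOD1.

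**The analysis.** Section 3.4.2 lists sNfL as an endpoint. Section 11 estimates the change in each measure over a period of up to 12 months and compares genetically defined groups on changes over time.

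**The concern.** The denser schedule is triggered by the genetic result alone, and its main component is a task that the patient performs on a smartphone. If it is given to a carrier who refused notification, the schedule itself can become a signal. The protocol explains why that matters: awareness of one's own result, with its implications for relatives, "might be perceived as psychologically burdensome". Elsewhere it guards disclosure with care, through written directives, staged counselling and sealed pseudonymized reports. Note 2 is not tied to any of these, and about 18 sites are left to decide for themselves whether a refuser goes on the SOD1 schedule.

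A smaller issue comes from the same note. sNfL continues after V2 in SOD1 carriers but not in the other groups, and section 11 does not say over which window the groups are to be compared.

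**Working it through.** **1. Text against text**

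- Trigger: SOD1 mutation (note 2). No directive is mentioned, and no pathogenicity class is given.
- Visible to the patient: yes for app ALS-FRS, because it is self-assessment. Not necessarily for sNfL, because existing values are collected.
- Who is covered: all SOD1 carriers, and therefore also those who chose no notification. Table 11 limits the therapeutic-relevance directive to likely pathogenic or pathogenic variants, so a carrier of an SOD1 variant of uncertain significance under that directive could be in the same position.
- Reconciling text: none found in note 2, sections 8.1, 8.2, 9.6.1, 12.3 or 12.5, or Tables 11 and 12. None of them limits the SOD1 schedule to those who permit notification, gives the same schedule to others, or masks it.
- Condition for inference: the participant must know or work out that the higher frequency is tied to SOD1.

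**2. Scale**

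The plan states no figure for this point, so there is none to reproduce. Inputs: 2,000 subjects (section 5.1); SOD1 mutations in 14.8% of fALS and 1.2% of sALS; C9orf72 expansions in 6.5% overall, 34% of fALS and 5% of sALS; sALS above 90% of patients (all section 2.1). With *f* the fALS share:

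expected SOD1 carriers = 2,000 × [0.148*f* + 0.012(1 − *f*)] = 24 + 272*f*

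- *f* implied by the C9orf72 figures: 0.34*f* + 0.05(1 − *f*) = 0.065, so *f* = 0.015 / 0.29 = 5.17%. Carriers = 24 + 272 × 0.0517 = 38.1.
- *f* = 10%, the limit set by sALS above 90%: carriers = 24 + 27.2 = 51.2.
- Rounding: if 5% of sALS stands for 4.5% to 5.5%, *f* runs from 0.010 / 0.285 = 3.5% to 0.020 / 0.295 = 6.8%, and carriers from 33.5 to 42.4. The 38 is therefore soft. Section 2.1 also says that fALS may be more frequent than expected, so 51 is not a ceiling.

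The documents give no refusal share. As scaling only, each 10% of carriers refusing is 3.8 to 5.1 people. The chance of at least one refusing carrier is 1 − (1 − *pr*)^2000, with *p* the carrier frequency and *r* an assumed refusal share among carriers. For *f* of 5% to 10% (*p* = 0.0188 to 0.0256):

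- *r* = 1%: 31% to 40%
- *r* = 5%: 85% to 92%
- *r* = 10%: 98% to 99%

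**3. sNfL windows**

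- Non-SOD1: V1 (M1–M3) and V2 (M4–M8). Nothing is planned later.
- SOD1: V1, V2 and V3 (M9–M14), with up to monthly values.
- The only planned window common to both is V1 to V2. Section 11 allows change over up to 12 months for each measure and does not restrict sNfL to that window.

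**The case against.** The best reply is that this is silence, not contradiction. Section 12.3.1 is categorical, and note 2 sets only a maximum frequency. A site can honour both by leaving refusers on the ordinary visits. Section 12.5 limits de-pseudonymization to authorized persons, and section 12.3.2 ties it to the participant's authorization. This is fair as far as it goes, but none of these passages governs scheduling, and nothing tells the site to leave refusers out.

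The harm is also conditional. Whether participants are told what the denser schedule means, or consent to it separately, would appear in consent pages that were not available. That stands, and it limits the claim to a possibility.

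A reader might infer a stark contrast between three assessments for everyone and about weekly entries for carriers. The documents do not support that comparison. Remote self-assessment is a general data source (sections 8.1 and 8.2), section 2.3.2 expects ALS-FRS to come through the app without a genotype restriction, and no cap on app use is stated for non-SOD1 patients. App use alone signals nothing. Any signal lies in a difference in frequency whose size is unknown.

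On sNfL, the objective is only to register available data, the study is exploratory, and without planned V3 values in non-SOD1 patients a direct V3 comparison cannot be made. That also stands. What remains is that the plan permits changes over unequal windows to be compared.

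**Conclusion.** The point holds as a gap between note 2 and section 12.3.1 that should be closed. Followed as written, note 2 can undercut a consent commitment, because it assigns a patient-visible task by genotype without regard to the directive.

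Its size is uncertain. About 38 to 51 SOD1 carriers are expected on the protocol's approximate figures, and only those whose directive does not permit the result to be given are affected. Their number is unknown. The conclusion rests on the text of note 2 and on the absence of a reconciling passage in the material available, not on a refusal rate.

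Two stronger readings are not supported. One is that the schedule discloses the result or that the consent form is deficient: inference needs knowledge that the participant may not have, and the form could not be checked. The other is that the sNfL comparison is biased: no bias size can be given, and the defect is only that section 11 leaves the window open. The monthly sNfL collection is no part of the disclosure concern. The primary endpoint, variant frequency, is not touched.

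**What to change.** **Note 2, reconciled with section 12.3.1.** Add: *The additional patient-facing collection in SOD1 carriers applies only to participants whose recorded directive permits notification of that SOD1 result, and does not start before the result has been communicated.* Tying the condition to the particular result also covers variants outside the classes in Table 11's therapeutic-relevance row.

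Cost: one sentence, and dense ALS-FRS data from fewer SOD1 carriers, by a number that cannot be stated. The directive is already required of every participant. A record that disclosure has taken place is not among the items in the section 9 tables, so sites need a way to confirm it before starting the schedule.

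**Section 11 (minor).** Add: *The between-genotype comparison of sNfL change uses V1 to V2 only; later sNfL values in SOD1 carriers are described within the SOD1 group.* Cost: one sentence. No contrast is lost that the planned schedule could support.

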## **8.2. Data collection**

Data will be collected from various sources and by different means. Some data are obtainable retrospectively as from medical records (at study sites) and platform-based registry (APST platform). Other data will be collected prospectively using on-site or assessments.

Data defined in the protocol will be assessed and captured by different means:

- Data from medical records and on-site assessments: data on clinical characteristics, family history, interventions and health care measures) will be collected on data sheets and transferred to predefined data fields on the web-based study software “studioMED+” or may be captured on the electronic case report form (eCRF) of “studioMED+” directly.
- Data from remote assessment: data from digital self-assessments (ALS-FRS, MYMOP) will be captured on a smart phone application (“ALS-App”) and stored in the data base of the APST platform (<https://www.ambulanzpartner.de/>). The “ALS-App” serves as a mobile application of the APST platform.
- Data from genetic laboratory: molecular genetic analysis will be performed on blood samples provided by study participant. Results from the genetic investigation will be generated by the genetic laboratory and transferred to predefined data fields on the web-based study software “studioMED+”.
- Data on health care measures: data on the provision with assistive technology (complex power wheelchairs, communication devices, robotic assistive systems, symptomatic pharmacotherapy, physical, occupational and speech therapy will be captured on the APST platform directly.

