## **11. Statistical methods and analysis plan**

Descriptive statistics will be presented for each assessment of all subjects at study visit. Subgroup analyses by genetic or clinical criteria or other baseline characteristics will be performed. Secondary endpoints in the genetically defined subsets of ALS with confirmed SOD1 or C9orf72 mutations will be compared to genetically tested patients with ALS not revealing any ALS-associated mutation in any of the tested genes. Descriptive statistics will be used for the statistical analysis (frequency in percentage, mean, median, standard deviation in  $\pm$ , interquartile ranges (Q1, Q3), and ranges (min, max). The standardized mean difference (SMD) will be applied in this study. The SMD of each measure over up to 12 months will be estimated using the change in measure between each subject's assessments and within each individual. The standardized mean difference expresses the size of intervention effect. Difference of frequencies between two groups will be assessed by Fisher's exact test or Chi-square test, or within metric data by using the Shapiro-Wilk test, Kruskal-Wallis test and Mann-Whitney U-test. The Wilcoxon test will be employed for the analysis of statistical power of ordinal-scaled data, while metric data were subjected to the t-test (ALS-FRS, MYMOP). This analysis applies to the comparison of genetically defined subsets of ALS (baseline characteristics and changes over time). The analysis of follow-up data is limited to complete

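### The SOD1 comparison is not tied to common visits: sNfL change can run to V3 in carriers but stops at V2 in everyone else, and the ALS-FRS rule is left open

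*Combined protocol and SAP*

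**What the plan says.** Section 1 (Table 1, footnote 2) sets a denser schedule for one genotype: "in subgroup of patients with SOD1 mutation data will be collected more frequently". For sNfL this means "up to monthly collection of existing data of sNfL". For function it means "up to weekly self-assessment of ALS-FRS using the ALS-App in addition to on-site assessment of ALSFRS-R during site visits". The rest of the cohort is treated differently for the biomarker: "In the main cohort of non-SOD1 patients the collection of sNfL data is limited to the visits V1 (baseline) and V2 (follow-up". The sNfL entry that Table 1 shows at V3 therefore applies to SOD1 carriers alone.

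Section 4.3 gives everyone the same backbone: "All subjects will undergo 3 assessments over a period of approximately 12 months". App capture is not reserved for SOD1 carriers. Section 8.1 lists as a general data source "Assessment and data capture from remote (digital self-assessment): self-assessment scales (ALS-FRS, MYMOP", and Section 8.2 says that "data from digital self-assessments (ALS-FRS, MYMOP) will be captured on a smart phone application".

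Section 11 compares the SOD1 and C9orf72 subsets with tested patients who carry no mutation in the four genes, both at baseline and over time. Its effect measure is defined as follows: "The SMD of each measure over up to 12 months will be estimated using the change in measure", taken between each subject's own assessments. Follow-up analyses use complete cases, and the covariates named for the longitudinal results are sex, age and intervention history. Section 11 does not say which assessments, which mode of capture or which interval enter the genotype comparison.

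**The concern.** A comparison of change between groups is interpretable when change is measured over the same interval, in the same way, in patients selected by the same rule. The schedule breaks the first condition for sNfL, and the analysis text protects none of the three for ALS-FRS.

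For sNfL, taking each subject's change over up to 12 months gives carriers a span that can reach V3 and gives comparators a span that ends at V2. For ALS-FRS, V1 to V3 scores are planned in every group. However, nothing stops an extra app score in a SOD1 carrier from serving as the follow-up value, or from making that carrier count as complete without the scheduled visit. At stake is whether a reported SOD1 difference in biomarker course or functional decline reflects genotype or the collection scheme. The primary endpoint, variant frequency, is not affected.

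**Working it through.** The plan states no power, effect size or SD, and its sample size rests on feasibility, so there is no figure of its own to reproduce.

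1. **Number of measurements over 12 months (Table 1, footnote 2).** ALS-FRS: up to 52 weekly app scores + 3 visits = 55 in SOD1 carriers, against 3 scheduled assessments in others; 55/3 is about 18 times as many. sNfL: up to 12 against 2.

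2. **sNfL time span.** The Table 1 windows are V1 M1–M3, V2 M4–M8 and V3 M9–M14. The comparator span, V1 to V2, is 4 − 3 = 1 month to 8 − 1 = 7 months. The SOD1 span, V1 to V3, is 9 − 3 = 6 months to 14 − 1 = 13 months. On the nominal timing in Section 4.3 (follow-up at 6 months, final assessment at 10 to 14), suppose sNfL changes by the same amount *s* per month in both groups. The apparent ratio of SOD1 to comparator change is then 10*s*/6*s* = 1.7 to 14*s*/6*s* = 2.3, and 12*s*/6*s* = 2 at 12 months. The absolute artefact at 12 months is 6*s*. The documents give no value for *s*; if sNfL is flat over time, the artefact is small. No comparator has a V3 sNfL value, so a 12-month complete-case contrast would have an empty reference group.

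3. **Size of the SOD1 group.** Section 2.1 gives SOD1 rates of 14.8% in familial and 1.2% in sporadic ALS, with sporadic cases above 90%. With an assumed familial share *f* of 5% to 10%, carriers = 2,000 × [(1 − *f*) × 0.012 + *f* × 0.148].
   - *f* = 5%: 2,000 × 0.0188 = about 38.
   - *f* = 10%: 2,000 × 0.0256 = about 51.
   - Among 1,000 completers (Section 5.1 expects more than that), with equal completion: about 19 to 26.

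4. **ALS-FRS with no genotype effect.** The inputs of this simulation are assumptions and are not in the documents: mean decline 0.9 points/month (SD 0.7), measurement SD 1.5, 50% completing 12 months, dropout ranging from unrelated to strongly related to slope, and an app-minus-site offset of 0, 1 or 2 points. SMD is SOD1 minus comparator; positive means less apparent decline in SOD1. Ranges run over the dropout settings.

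| Follow-up value used for SOD1 (comparator: on-site V3 completers) | Offset 0 | Offset 1 | Offset 2 |
|---|---|---|---|
| On-site score at the common visit | 0.00 | not applicable | not applicable |
| App score at month 12, completers | 0.00 | 0.12 to 0.19 | 0.25 to 0.38 |
| Last app score of all carriers, total change | 0.23 to 0.32 | 0.41 to 0.45 | 0.57 to 0.60 |
| Last app score of all carriers, change per month | −0.22 to 0.00 | 0.00 to 0.17 | 0.23 to 0.33 |

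   Frequency alone does nothing: with the same interval, the same completers and no offset, the SMD is 0.00. Each non-zero entry comes from a difference in mode, interval or completer rule, and its sign depends on the metric.

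5. **Effect on a test.** With 25 SOD1 against an assumed 900 comparators, two-sided 5%, power is about 32% for an SMD of 0.3 and 69% for 0.5. With 51 carriers it is about 55% for 0.3. If an SMD of 0.3 is pure artefact, those are roughly the chances of a nominally significant result with no genotype effect.

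**The case against.** The strongest reply is that the plan does not force any of this on the ALS-FRS. The app scores are added to visit scores and do not replace them, and all patients share three assessments. The progression rate in Section 9.6.2 uses a single score, so the number of assessments does not enter it. The study is exploratory with no formal hypothesis. For sNfL, a V1 to V2 change fits within a period of up to 12 months, the footnote openly limits non-SOD1 collection, and Section 3.3 lists sNfL as data to be registered, apart from the genotype comparison.

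Much of this stands, and it rules out several stronger readings that a reader might infer:

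- *That app scores occur in one group only.* Sections 8.1 and 8.2 describe remote capture for the whole study. The documented asymmetry is weekly frequency; the app share among comparators is unknown.
- *That a carrier who dies between V2 and V3 contributes late decline while a similar non-carrier is dropped.* On its natural reading, the complete-case rule in Section 11 drops both.
- *That denser measurement itself biases change.* It does not (step 4).
- *That the bias is 0.5 to 15 points.* That range multiplies the V2–V3 gap (9 − 8 = 1 to 14 − 4 = 10 months) by an assumed 0.5 to 1.5 points/month. It is one patient's possible decline, not a difference between groups.

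The rest does not stand. Section 3.4.2 lists sNfL among the endpoints on function and progression, and Section 11 applies its SMD to each measure and compares the genetic subsets. Section 11 also reports p-values against 5% and confidence intervals, so exploratory status does not protect a reader from a spurious difference. Although the progression rate uses one score, the plan does not say which one.

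**Conclusion.** The point holds in two parts of different strength. For sNfL the mismatch in time span is built into the schedule: a like-for-like 12-month contrast of SOD1 carriers with mutation-negative patients cannot be made, and the plan does not limit the comparison to V1–V2. Under a common constant monthly change, the apparent SOD1 change would be about twice the comparator's (1.7 to 2.3 times on the Section 4.3 timing). The absolute size depends on a monthly change that the documents do not give.

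For ALS-FRS, bias is a risk that the text leaves open, not a consequence of the design. It is zero on common visits. Under the assumptions in step 4 it reaches an SMD of about 0.2 to 0.3 in either direction without any mode offset, and more in some cases with one. That matters with only some 19 to 26 SOD1 completers. The C9orf72 versus mutation-negative contrast is unaffected, because both groups follow the non-SOD1 schedule. This should be settled before analysis, but it does not threaten the primary objective.

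**What to change.** Add to Section 11:

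- sNfL change is compared between SOD1 and mutation-negative patients from V1 to V2 only.
- Between-genotype comparisons of ALS-FRS and progression rate use the scheduled V1, V2 and V3 assessments in every group, and a case is complete or not by those visits alone.
- At each visit the on-site score is used where there is one; otherwise a remote score within the visit window is used, under the same rule in all groups. Mode is recorded, and an on-site-only analysis is run as a sensitivity analysis.
- The additional weekly app and monthly sNfL data serve only to describe SOD1 carriers or for sensitivity analyses.

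An outright restriction to on-site scores is not advised as the main rule: it would discard remote visit scores in every group and could lose patients who cannot attend.

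The cost is a few lines of analysis text and a recorded field for mode. The extra SOD1 measurements will not sharpen the between-group contrast, and the sNfL comparison will cover about 6 months instead of 12.
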